PROTOCOL TITLE	Open multi-centre study to evaluate efficacy of adding Polyoxidonium® lyophilizate to a complex therapy of hospitalized patients with COVID-19.
STUDY PERIOD	2020
STUDY AIM	To evaluate safety and efficacy of Polyoxidonium® (azoximer bromide) as an

addition to complex treatment of hospitalized patients with COVID-19.

KEY OUTCOMES

EFFICACY OUTCOMES

SAFETY AND EFFICACY

PRIMARY EFFICACY ENDPOINT

Subject clinical status using the WHO 7-point ordinal scale on day 15 as compared to baseline.

1. Not hospitalized, no limitations on activities.
2. Not hospitalized, limitation on activities.
3. Hospitalized, not requiring supplemental oxygen.
4. Hospitalized, requiring supplemental oxygen.
5. Hospitalized, on non-invasive ventilation or high flow oxygen devices.
6. Hospitalized, on invasive mechanical ventilation or ECMO
7. Death.

SECONDARY EFFICACY ENDPOINTS

Clinical severity assessed on scales

1. *Subject clinical status using the WHO 7-point ordinal scale:*
 - Time to improvement of each parameter of the primary scale from admission.
 - Subject clinical status at days 3, 5, 8, 11, and 29.
 - Average change in the clinical status at days 3, 5, 8, 11, 15, and 29 as compared to baseline.
2. *The NEWS Score (National Early Warning Score) describes the vital signs (pulse rate, breathing rate, temperature, blood pressure etc.) and its deviation from the reference ranges): is evaluated daily and on day 15.*
 - The time to discharge or to a NEWS of ≤ 2 and maintained for 24 hours, whichever occurs first.
 - Change from baseline to days 3, 5, 8, 11, 15, and 29 in NEWS.
3. *Oxygenation, including mechanical ventilation:*
 - Change (day by day) in the need for oxygenation in the first 28 days (up to day 29).
4. *Hospitalization*
 - Duration of hospitalization (days).
5. *Mortality (date, cause)*
 - 28-day mortality.
6. *SOFA scale (evaluation of organ failure associated with sepsis): is evaluated daily and on day 15.*
 - Change from baseline to days 3, 5, 8, 11, 15, and 29 in SOFA.

SAFETY OUTCOMES

- Cumulative incidence of serious adverse events/reactions (SAEs, SARs).
- Cumulative incidence of adverse events/reactions (AEs, ARs).
- Permanent or temporary discontinuation of infusions/injections (by any cause).
- Clinically significant changes in the levels of leukocytes, haemoglobin, platelets, creatinine, glucose, total bilirubin, ALT, AST, CRP, and other parameters.

STUDY DESIGN

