Open multi-centre observational study of efficacy and safety of a medicinal

	
product.
 
The clinical efficacy will be assessed by changes in the patient's clinical status, duration of hospitalization, oxygenation/mechanical ventilation. The clinical examination will include clinical, laboratory, and instrumental investigations according to the current guidelines on treatment of COVID-19 in the Russian Federation.

POPULATION	Hospitalized patients of 18 years and older with confirmed COVID-19.
SAMPLE SIZE	At least 50 patients
TREATMENT ALLOCATION	All study subjects will receive treatment with Polyoxidonium, lyophilizate, 12 mg, in addition to the standard treatment
DIAGNOSIS	Verified COVID-19

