3. AIM AND OBJECTIVES OF THE STUDY

3.1. Study Aim

To evaluate safety and efficacy of Polyoxidonium® (azoximer bromide) as an addition to complex treatment of hospitalized patients with COVID-19.

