4.2. Type/design of the study

This study is an open multi-centre observational study evaluating the efficacy and safety of a non-interventional drug.

The design of a non-invasive non-interventional study was chosen to evaluate the efficacy of the drug in routine clinical practice. Since this study will be non-interventional, all procedures will be carried out in strict accordance with the standards of routine clinical practice and meet the non-interventional criteria set by the Good Pharmacovigilance Practice of the Eurasian Economic Union [approved by the decision of the Council of the Eurasian Economic Commission dated 03.11.2016 No. 87].

No	CRITERION	CONTENT
1	Object, MA	Drug products approved for human use; with a valid marketing authorization
2	Rationale for prescription	As judged by the doctor within the routine clinical practice
3	Time of prescription	Prior to inclusion in the study and regardless of the decision to participate
4	Requirements to the prescription	According to the approved therapeutic indications (therapeutic indications, dosage, etc.)

According to the current routine practice, up-to-date and widely accepted

5	Patient management	clinical guidelines and guides According to the protocol, however, the intervention in the routine management of the patient is minimal
6	Randomization, blinding	Not applicable

The clinical efficacy will be assessed by changes in the patient’s clinical status, duration of hospitalization, oxygenation/mechanical ventilation. The clinical examination will include clinical, laboratory, and instrumental investigations according to the current guidelines on treatment of COVID-19 in the Russian Federation. No additional procedures, except for the special scales (non-invasive), will be carried out during the planned non-interventional study.

The overall objective of the study is to evaluate the clinical efficacy of the investigational product in adult patients hospitalized with COVID-19. The primary endpoint is the patient’s clinical status (in a 7-point ordinal school) on day 15 in accordance with the WHO Master Protocol¹.

The study will be conducted in the clinical centre during hospitalization and outpatient visits of patients to the clinical centre, if necessary.

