Patients who meet the inclusion criteria and do not meet any of the exclusion criteria will be included in a single study group, that will receive Polyoxidonium®, lyophilizate for solution for injections and topical application, 6 mg (NPO Petrovax Pharm LLC, Russia) in dose of 12 mg once daily intravenously (IV) for 3 days, then every other day intramuscularly (IM) on days 5–17 (the total treatment course is 10 injections).

The data collected in this observational program should help doctors find more effective therapy for other patients with COVID-19.

The study will include the following periods:

- **Treatment period** (17 days in total, days 1...17, if the study criteria are met) with administration of the investigational product (IP) (intravenous injections for 3 days, then intramuscular injections for 14 days), assessment of the clinical status, recording of AEs.

- **Follow-up period** (days 18...29±3)

Figure 4.1 shows the study flow chart.

[figure not shown]

Figure 4.1. Study flow chart

¹ MASTER PROTOCOL. A Multi-centre, Adaptive, Randomized, Double-Blind, Placebo-Controlled Clinical Trial of the Safety and Efficacy of Investigational Therapeutics for the Treatment of COVID-19 in Hospitalized Patients. Electronic source Free access: <https://www.who.int/blueprint/priority-diseases/key-action/multicenter-adaptive-RCT-of-investigational-therapeutics-for-COVID-19.pdf>. Access date: March 13, 2020

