9.7.2.2. Analysis of the secondary efficacy endpoints

The interval (quantitative) data will be described with arithmetic mean, standard deviation, median, lower quartile (25%) and higher quartile (75%), minimum, maximum, coefficient of variation, and 95% confidence interval for the mean. The categorical (qualitative) data will be described with incidences, percentage, or proportions, and 95% confidence interval for percentage or proportions.

The time to event data will be processed via survival analysis with the use of Kaplan-Meier curves and 95% confidence intervals.

The following standard parametric tests are planned for comparison of quantitative data with normal distribution: Student t-test for dependent/independent samples, analysis of variance (ANOVA) for repeated measurements.

The following standard non-parametric tests are planned for comparison of quantitative data with distribution other than normal: Mann-Whitney U-test, Wilcoxon T-test, Friedman test.

Shapiro-Wilk test will be used to test normality of the distribution.

The incidences will be compared between the treatment groups with Pearson's χ^2 -test or Fischer's exact test.

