9.7.3. Statistical methods for analysis of safety of the investigational product

Safety analysis will be performed in the safety population. Regardless of the reason for the completion of the study, the data of all patients who received at least one infusion according to the assignments will be included in the safety analysis.

Safety data will be analysed using the methods chosen for efficacy analysis.

Incidences of adverse events/serious adverse events will be calculated for assessment of AEs. Incidences of adverse events reported during the study will be presented as number of patients with AE in total and in each treatment group. Also, number of AEs per each severity category and per causal relationship with the study drug will be presented.

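### All patients form one treated group with no control or benchmark, so the between-group test in 9.7.2.2 cannot be run and change from baseline cannot show what adding the drug achieves

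*Combined protocol and SAP*

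**What the plan says.** **Design.** The synopsis states under treatment allocation: "All study subjects will receive treatment with Polyoxidonium, lyophilizate, 12 mg, in addition to the standard treatment". Section 4.2 says that eligible patients "will be included in a single study group". Inclusion criterion 1 (5.1) requires Polyoxidonium to be already taken or prescribed, so an untreated patient cannot enter. Randomization is marked not applicable (4.2, 4.3.2). The synopsis also gives all patients guideline COVID-19 treatment.

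**Question asked.** The title is "Open multi-centre study to evaluate efficacy of adding Polyoxidonium" to complex therapy. The aim in 3.1 is "To evaluate safety and efficacy of Polyoxidonium". Section 4.2 adds: "The overall objective of the study is to evaluate the clinical efficacy of the investigational product". Section 11.9 requires the report to reach a plain conclusion on efficacy as well as safety.

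**Analysis.** Where the primary endpoint has a contrast, it is Day 15 against baseline on the 7-point scale (synopsis, 4.1, 7.1, 9.1). No test is named for it. For the secondary endpoints, 9.7.2.2 says "The incidences will be compared between the treatment groups with" Pearson's chi-square or Fisher's exact test, and lists a "Student t-test for dependent/independent samples" and the Mann-Whitney test. Section 9.7.3 presents the "number of patients with AE in total and in each treatment group". Section 9.9 allows a treatment effect to be evaluated across subgroups, with interaction tests.

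**The concern.** Two things do not fit a single treated group.

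First, a comparison of treatment groups needs at least two of them. Section 9.7.2.2 plans one that the design cannot supply. Two-arm wording also remains in 2.4.2 (an active group, and two groups of patients) and in 2.5 (a comparator supplied by the sponsor).

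Second, and of more consequence, the question in the title concerns what the drug adds to other therapy. Answering it needs some estimate of how such patients fare on that therapy alone, and the plan contains none. Hospitalized patients tend to change over two weeks for reasons other than the drug. Section 9.7.2.1 itself allows that all patients with mild disease may be back to normal activity by Day 15, and does not credit the drug with that. If the plan is followed, a significant change from baseline could be reported as efficacy when it shows only that patients changed over time.

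**Working it through.** **1. Can the planned comparison be run?** Take 35 improved and 15 not improved as an assumed result for the 50 treated patients, and an empty second row for the missing group.

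- Chi-square: the expected count is row total × column total / N. For the second row this is 0 × 35 / 50 = 0 and 0 × 15 / 50 = 0. The term (O − E)² / E is then 0/0, so the statistic is undefined.
- Fisher: with a row total of 0 only one table is possible, so p = 1 and the odds ratio is undefined, whatever the data.

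The synopsis and 9.1 give the same chi-square/Fisher sentence without mentioning treatment groups, so 9.7.2.2 is the outlier. In 9.7.3 the by-group display is merely redundant: with one group it equals the total.

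**2. What does change from baseline estimate?** Observed change = natural course + effect of background therapy + any effect of the drug. All three act on every patient, and the plan observes only the sum. Splitting by baseline severity (9.7.2.1) gives two sums with the same three parts, because both strata are fully treated. A subgroup contrast under 9.9 is a difference between such sums.

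**3. How far could this mislead?** Illustration only. The documents give no recovery rates, so the rates, step sizes and baseline mixes below are assumptions.

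Inputs: n = 50 (the synopsis minimum); significance level 0.05 (9.8, which does not state sidedness; two-sided is assumed); Wilcoxon signed-rank test (listed for secondary endpoints; none is named for the primary); zero drug effect. Zeros are dropped and the tie-corrected normal approximation is used, with 20,000 simulated studies per cell. The baseline mixes for categories 3/4/5/6 are 50/30/15/5% and 30/40/20/10%. Step sizes are equally likely up to the stated maximum and are kept within the scale. Each cell shows the chance of a significant improvement, as a range over the two mixes.

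| Maximum step (improve / worsen) | 40% improve, 20% worsen | 60% improve, 15% worsen | Equal (20/20 or 30/30) |
|---|---|---|---|
| 2 / 3 | 21-25% | 84-87% | about 1% |
| 3 / 3 | 31-41% | 91-95% | 2-3% |
| 2 / 2 | 41-42% | 95-96% | about 3% |
| 1 / 1 | 46% | 98% | about 3% |

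The last row can be checked by hand. If every change is one category, all ranks are equal and the statistic reduces to z = (I − W) / √(I + W), where I and W are the numbers improving and worsening.

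- 40/20: I = 20, W = 10, expected z ≈ 10 / √30 = 1.83, close to the critical 1.96, so a little under half of studies are significant.
- 60/15: I = 30, W = 7.5, expected z ≈ 22.5 / √37.5 = 3.67, so nearly all are.
- Equal: expected z = 0, so about 2.5% fall in the improvement direction.

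The drug effect is zero throughout. The p-value follows the assumed natural course and background therapy.

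**4. Is the limitation declared?** Section 4.3 calls the limitations typical of observational work and discusses selection, missing data and withdrawal. It does not name the missing control or natural recovery.

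**The case against.** The uncontrolled, non-interventional design is deliberate and openly stated. The phrase in 9.7.2.2 may be only a drafting leftover, since two parallel passages lack it. Section 11.9 asks for a clear conclusion but not a favourable one, and a report saying that the effect cannot be separated from natural course would comply. Section 2.4.1 concedes that the drug may not help an individual patient, section 9.9 is permissive, and the aim and objectives do not say relative to standard therapy.

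Much of this stands. The group wording alone would be editorial. The non-interventional label explains why there is no randomization or blinding, but it does not supply a reference for an efficacy conclusion. The title does ask about adding the drug, and nothing in the plan tells the report writer that this question is out of reach.

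Four stronger readings are tempting but not supported:

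- That the independent-samples t-test and Mann-Whitney test have nothing to compare. Baseline severity (9.7.2.1) and the 9.9 subgroups are independent groups. The gap is that the plan does not link the tests to them, and such contrasts would not estimate a drug effect.
- That a subgroup difference would be prognosis alone. It would mix prognosis, background therapy and any drug effect in unknown shares.
- That a within-patient test is invalid. It is a valid test of change over time, but it answers a different question.
- That the risk of a misleading result can be stated closely. The table shows how much it moves with assumed step sizes.

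**Conclusion.** Wrong as written. The comparison between treatment groups in 9.7.2.2 cannot be carried out. The efficacy conclusion that the title, aim and 11.9 point to cannot be supported by Day 15 against baseline in patients who all receive both the drug and guideline therapy. The second part carries the weight.

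The size is structural: 0 control patients and no external benchmark. This rests on the documents alone. The illustrative chances of a significant improvement without any drug effect (about 21-46% at 40/20, about 84-98% at 60/15, about 1-3% when improving and worsening are equally frequent) rest on assumed rates, step sizes and baseline mixes, and on a test that the plan does not assign to the primary endpoint. They show direction and sensitivity and do not predict this study. None of this says that the drug is ineffective, or that a single-group study has no descriptive value.

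**What to change.** - **Title, synopsis, 3.1, 3.2, 4.2, 9.7.2 and 11.9:** restate the efficacy objective as describing change in clinical status during treatment. State that no conclusion on efficacy relative to standard therapy will be drawn.
- **4.3:** name the missing control and natural recovery as limitations.
- **9.7.2.1:** report the Day 15 category distribution and the proportion improving by at least one category with an exact 95% CI, overall and by baseline severity. For scale, 35/50 would give 70% (55% to 82%). The severity definitions (synopsis, 5.1) overlap at SpO₂ 94% and respiratory rate 24 and must be reconciled first. Label any within-patient test as a test of change over time.
- **9.7.2.2:** delete the reference to treatment groups. Here, in the synopsis and in 9.1, limit the independent-sample tests to named baseline subgroups.
- **9.7.3:** report adverse event incidence for the single group with exact 95% CI.
- **9.9:** replace the treatment effect and interaction tests with descriptive outcomes by subgroup.
- **2.4.2 and 2.5:** remove the two-arm wording.

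The cost is a weaker headline claim and an amendment under 11.7, with ethics committee approval because the scientific value of the study is affected. No new data are needed. A concurrent untreated comparator is not proposed, since it would require changing inclusion criterion 1 and collecting more data. An external benchmark would leave eligibility alone, but the documents offer no source for one. How missing Day 15 data are handled (9.4) is a separate point.

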9.7.3. Statistical methods for analysis of safety of the investigational product

Safety analysis will be performed in the safety population. Regardless of the reason for the completion of the study, the data of all patients who received at least one infusion according to the assignments will be included in the safety analysis.

Safety data will be analysed using the methods chosen for efficacy analysis.

Incidences of adverse events/serious adverse events will be calculated for assessment of AEs. Incidences of adverse events reported during the study will be presented as number of patients with AE in total and in each treatment group. Also, number of AEs per each severity category and per causal relationship with the study drug will be presented.

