8. ASSESSMENT OF SAFETY

8.1. Safety outcomes

The safety will be evaluated throughout the study (from signing the informed consent to the study completion visit) based on the following:

Safety outcomes

Safety parameters

- Cumulative incidence of serious adverse events/reactions (SAEs, SARs)
- Cumulative incidence of adverse events/reaction (AEs, ARs)
- Permanent or temporary discontinuation of infusions/injections (by any cause)
- Clinically significant changes in the levels of leukocytes, haemoglobin, platelets, creatinine, glucose, total bilirubin, ALT, AST, CRP, and other parameters.

The safety of the investigational product will be evaluated based on statistical analysis of the specified parameters.

The investigator is responsible for notifying the Sponsor of any event that seems unusual, including the deviation of the patient's test results from normal values, even if this event can be considered as an unforeseen benefit for the patient.

8.2. Methods and deadlines for assessing, recording, and analysing safety and tolerability outcomes

Surveys related to safety assessment are carried out in accordance with the schedule of the study procedures and a description of the study parts.

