9.8. Level of significance

The significance level will be 0.05 (5%).

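### Laboratory safety data go to the efficacy methods with no worsening-only, per-patient analysis, so tests of change, if reported, can hide a serious rise in a minority

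*Combined protocol and SAP*

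**What the plan says.** The laboratory safety outcome in section 8.1 (also in the synopsis and 4.1) is "Clinically significant changes in the levels of leukocytes, haemoglobin, platelets, creatinine, glucose, total bilirubin, ALT, AST, CRP, and other parameters". Section 8.1 adds: "The safety of the investigational product will be evaluated based on statistical analysis of the specified parameters".

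For the method, 9.7.3 states: "Safety data will be analysed using the methods chosen for efficacy analysis". The rest of 9.7.3 concerns adverse events: patients with an AE, and AEs by severity and by causal relationship. No laboratory analysis is described.

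The imported methods are in 9.7.2.2:
- **Tests for normally distributed data:** "Student t-test for dependent/independent samples, analysis of variance (ANOVA) for repeated measurements".
- **Tests otherwise:** "Mann-Whitney U-test, Wilcoxon T-test, Friedman test".
- **How the choice is made:** "Shapiro-Wilk test will be used to test normality of the distribution".
- **Categorical data:** "The categorical (qualitative) data will be described with incidences, percentage, or proportions, and 95% confidence interval for percentage or proportions".
- **Descriptive statistics:** these include the minimum and maximum.

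Section 9.8 sets the level at 0.05 without stating sidedness. Section 4.2 has one study group, so a laboratory test of change is a within-patient comparison. Section 8.3.1 allows an abnormal laboratory finding to be an AE and requires capture of Grade 3 and 4 AEs. Section 8.3.4 adopts the DAIDS grading table, version 2.1.

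**The concern.** Drug harm to the liver, kidney or blood counts would probably appear as large changes in a few patients. The trial enrols hospitalised COVID-19 patients, many of whom should recover, so the average and the bulk of the ranks would move the other way. A test of average or rank change then answers a different question from the safety one, which is how many patients got materially worse.

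The outcome's wording does not settle this. It speaks of changes without naming a direction, and CRP is on the list, so a CRP fall as the infection clears fits the wording of a safety outcome. It gives no threshold, grade or rule on worst versus scheduled value. Section 9.7 leaves the usability of several methods to be judged after the data are collected, so what gets counted could also be settled then.

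At stake is section 11.9, which requires a clear conclusion on the safety profile. A reported laboratory p-value could look reassuring whether or not a minority was harmed.

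**Working it through.** The plan gives no effect size, SD, laboratory event rate or power, so there is no figure of its own to reproduce. The check asks whether the stated tests can mask harm in a minority.

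**Inputs from the documents.** N = 50 (synopsis: at least 50); single group (4.2); Shapiro-Wilk choosing between t-test and Wilcoxon (9.7.2.2); level 0.05 (9.8), taken as two-sided.

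**Assumed inputs, model 1 (ALT).** Baseline median 40 with log-SD 0.5; within-patient log-change SD 0.4; a background log-fall f in everyone; harm is a six-fold rise (log 6 added) in 4% or 10% of patients. Raw change = exp(b + c) − exp(b). There were 4,000 simulated trials per scenario.

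| Background fall, 1 − exp(−f) | Significant worsening, 4% / 10% harmed | Significant improvement, 4% / 10% harmed |
|---|---|---|
| none (f = 0) | 16.2% / 35.0% | not tabulated |
| about 10% (f = 0.1) | 0.6% / 4.7% | not tabulated |
| about 18% (f = 0.2) | 0.0% / 0.2% | 48.4% / 17.8% |
| about 26% (f = 0.3) | not tabulated | 88.8% / 52.4% |

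The test therefore fails to show worsening in 100 − 16.2 = 83.8% and 100 − 35.0 = 65.0% of trials even with no background trend.

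**Model 2, different assumptions.** Of 50 patients, k rise by a mean of 150 units (SD 40) and the rest fall by a mean of 10, 15 or 20 (SD 20). Shapiro-Wilk rejected normality in essentially every run, so the rule chose Wilcoxon. With k = 3 it gave a significant decrease in 60%, 96% and 100% of runs; with k = 5, in 22%, 78% and 99%. With k = 5 and no change in the rest, the increase was detected in 17%. The t-test is less easily misled: at k = 5 or more it never showed a significant decrease. With k = 8, a rise of 250 and the rest falling by 10, it detected the increase in 87% of runs, but the plan's rule would not have selected it.

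**Limits of the mechanism.** A uniform shift of 0.5 SD in all patients would be found: noncentrality 0.5 × √50 = 3.54, power 93%. The weakness is specific to harm concentrated in a minority. In the other direction, a natural CRP fall of 1 SD of the change (1 × √50 = 7.07) is significant in more than 99.9% of trials with no drug effect.

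**Per-patient counting.** The chance of at least one affected patient is 1 − (1 − p)^50: 1 − 0.96^50 = 87.0% and 1 − 0.90^50 = 99.5%. Exact 95% CIs are 0.5% to 13.7% for 2/50 and 3.3% to 21.8% for 5/50. This is not a like-for-like contrast with a significance test. It shows only that a count keeps the affected patients visible.

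**The case against.** The strongest reply is that the plan is broader than its tests. Clinically significant changes reads naturally as a per-patient judgement, which under 9.7.2.2 would be an incidence with a 95% CI. The maximum would expose an outlier: in model 2, with 3 to 5 patients rising by 150, the average largest change was about 184 to 197 units. Section 8.3.1 captures Grade 3 and 4 AEs, 9.7.3 counts AEs by severity, and 8.1 asks investigators to notify the sponsor of test results that deviate from normal.

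This stands as far as it goes, and it rules out a stronger reading. A reader might infer that laboratory safety rests only on tests of average change, that serious rises would disappear, or that p > 0.05 would be taken as proof of safety. The documents support none of these: other outputs are imported as well, serious rises have an AE route, and no section ties the safety conclusion to a p-value.

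The safeguards still leave gaps:
- An incidence needs a definition of the event, and there is none.
- A maximum shows one patient, not how many worsened from baseline.
- The capture commitment in 8.3.5 names only Grade 3 and 4 AEs and SAEs. The investigator paragraph below it speaks of all AEs, so a shift from Grade 0 to Grade 2 is not assured of being counted.
- Section 8.3.5 also records a laboratory abnormality belonging to a syndrome as the diagnosis, which removes the parameter from view.

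**Conclusion.** The point holds as a gap in specification with a demonstrable consequence. Section 9.7.3 names no worsening-only, per-patient laboratory analysis. If the quantitative tests are what is reported, they can return a null or favourable result while a minority is seriously worse. The masking appears in two differently built simulations. Its size depends on assumed values: in model 1, with a background fall of about 18%, worsening is shown in 0.0% to 0.2% of trials and improvement in 18% to 48%. The baseline, SDs, rise, fall and affected fraction are all assumptions, as is two-sided testing.

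The AE route gives real but partial protection. This is a change that should be made because it is cheap and closes identifiable gaps. It does not show that the plan would miss harm altogether.

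**What to change.** In 9.7.3, add a laboratory paragraph to this effect:

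*For each section 8.1 parameter that is measured and has a grade in the adopted DAIDS table, baseline grade is tabulated against worst post-baseline grade. The number and percentage of patients who worsen (for example by at least 2 grades, or to Grade 3-4) are reported with an exact 95% CI, in the harmful direction only. Mean changes and their p-values are descriptive, and no safety conclusion is based on them.*

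The 2-grade cut is an example. The sponsor should fix the cut and the harmful direction for each parameter before the data are seen. The DAIDS table is not reproduced in the documents, so which parameters it grades must be checked. For any ungraded parameter (CRP, if so), count only increases from baseline as safety findings. Reconcile haemoglobin, which is listed in 8.1 but absent from the haematology panels in 6.3.5 and the notes to Table 1.

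The cost is SAP wording and a few extra tables from laboratory tests already scheduled, plus whatever the haemoglobin reconciliation requires. Confidence limits at N = 50 will be wide (2/50 has an upper limit of 13.7%), and a single arm still cannot separate drug harm from disease progression.
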